The PACE study (AHRQ K12HS023011) compared weight loss programs that started either before knee replacement (PACE) or started 12 weeks after surgery (Delayed PACE). Sixteen patients were randomized (63.3±7.5 years old, 69% female, 69% White, BMI of $36.5 \pm 5.1 \text{ kg/m}^2$) to PACE or Delayed PACE. Primary outcomes from 11 participants were objectively assessed at 26 weeks after surgery. Nine participants provided self-reported outcomes at approximately 12.78±1.5 months after knee replacement. Participants in Delayed PACE lost significantly more weight (-7.6±5.9kg, -7.9±5.9%) than PACE (-2.5±2.7kg, -2.6±2.6%) at 26 weeks ($P=0.03$). Delayed PACE maintained greater weight loss outcomes than participants in PACE at one year post-operatively. Pain intensity decreased ($P<0.001$) and function improved ($P=0.001$) significantly, but no significant changes were observed in physical activity (Table 1).

Table 1. Physical Activity Pre- and Post-Surgery in PACE (n=6) & Delayed PACE (n=7)

	Baseline	12 Weeks	26 Weeks
Bouted MVPA, min/week			
PACE	81.2±141.8	3.5±5.4	33.3±76.4
Delayed PACE	37.6±85.7	62.1±135.8	78.1±108.0
Steps/day			
PACE	5715.7±3098.0	4255.6±1687.8	4991.8±2910.2
Delayed PACE	6062.4±2817.6	4943.6±1653.2	6324.4±2201.3

The research team has experience with recruitment of TKR patients in the Columbia, SC area. Currently, we have recruited 12 patients who underwent a TKR to participate in an ongoing study examining the use of Fitbits and social support on physical activity over a 4-month period. To date, 73% of patients recruited for this study are from the Columbia, SC region. Additionally, across the 5 orthopedic surgeons within the Palmetto Health USC Orthopedic Center, an average of 21.8 TKR are completed each week.

3) Objectives / Research Aims

The purpose of this proposed project is to conduct a pilot randomized controlled trial to examine the feasibility and preliminary efficacy of a physical therapist led physical activity intervention on physical activity levels in TKR patients after surgery. The specific aims of the project are:

Aim 1: To examine the feasibility and acceptability of conducting a randomized controlled trial examining a physical therapist led physical activity intervention for TKR patients within an outpatient physical therapy facility. Specifically, enrollment, retention, session attendance and duration, treatment fidelity, and patient and physical therapist satisfaction will be examined.

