Assessments will be completed before the second outpatient therapy session (baseline) and at 12 weeks after TKR. Detailed descriptions and a timeline of outcomes are provided below in the text and Table 2. Briefly, at both assessments, participants will be asked to complete surveys (demographics, brief medical history, KOOS, PROMIS, self-identification), which should take approximately 20 minutes to complete. Based on participant preferences, surveys will be able to be completed on paper or online via RedCAP, with the exception of the PROMIS surveys which are computer adaptive surveys. Participants will also be given an Actigraph Link accelerometer and ActivPAL monitor to wear for 7 days at each assessment. These monitors will be provided at the in-person assessment or mailed to the participants. At the end of the 7 days, these monitors will be returned to the PT clinic or participants will be provided with a prepaid padded envelope to return the monitor. Only at 12 weeks will participants complete functional tests and the Surgery and Medication Questionnaire, which will take approximately 15 minutes to complete. In the event participants are unable to complete the function tests at the in-person assessment, we will ask participants to complete the chair stand test at home and self-report the outcomes. Participants will not be asked to complete the 6-minute walk or timed up and go at home. Participants will receive \$20 for completing the 12-week assessment.

Measure	Baseline	12 Weeks
Participant Demographics	X	
Participant height and weight	X	X
Brief Medical History	X	X
Knee Injury and Osteoarthritis Outcome Score (KOOS)	X	X
PROMIS Pain Intensity, Pain Interference, & Mobility	X	X
WOMAC Pain and Stiffness	X	X
Physical Function		
6-minute walk		X
Timed up and go		X
Chair stands		X
Physical activity (Actigraph)	X	X
Sedentary time (ActivPAL)	X	X
Self-Reported Exercise Identity	X	X
PATH Study Survey		X

Primary Outcomes: The feasibility and acceptability of conducting a randomized controlled trial within an outpatient physical therapy setting is the primary endpoint. Specifically, we will examine the number of participants enrolled vs. approached, participant retention, number of therapy sessions attended, session duration, and treatment fidelity. Further, participants will complete a PATH Study Survey at the 12 week assessment. Physical therapists will complete a brief evaluation about delivering the PATH program.

Secondary Outcomes:

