- Self-reported exercise identity will be assessed at baseline and 12-week assessments using the Self-Reported Exercise Identity Scale.³³ Participants will rate on a scale from 1 (strongly disagree) to 5 (strongly agree) their feelings relating to exercise identity. Examples include, “I would feel a real loss if I were forced to give up exercising” and “I need exercise to feel good about myself.”

g. Procedures Involved

Design Overview: We propose to conduct a pilot two-arm cluster randomized controlled trial with patients attending outpatient physical therapy following TKR. The proposed project was developed in collaboration with [name], Senior Physical Therapist at Palmetto Health USC Orthopedic Center. Over 9 months, TKR patients (n=50) attending outpatient physical therapy at Palmetto Health USC Orthopedic Center will be recruited and randomized to either 1) PATH-12 (control), or 2) PATH. Due to potential contamination of the intervention between patients in PATH-12 and PATH during typical open, group-like physical therapy settings, we have opted to randomize physical therapy sites instead of individual patients. Specifically, physical therapy sites will be randomized to either Immediate or Delayed. The first phase of the study will take place starting in November and end after 25 participants have been recruited. During this time, those sites randomized to Immediate will receive the PATH intervention and those sites randomized to Delayed will receive the PATH-12 intervention. There will then be a “wash out period” to allow for all the participants to finish their current PT. After this “wash out period”, the second phase of the study will begin and will end after 25 participants have been recruited. During this time, those sites randomized to Immediate will receive the PATH-12 intervention and those sites randomized to Delayed will receive the PATH intervention.”

Screening: Participants will be required to complete a brief screening after the first physical therapy appointment. Research staff will administer the screening in-person or over the telephone. The screening will assess eligibility criteria and willingness to participate. Following the completion of the screener, eligible and interested participants will be invited to complete the informed consent process.

Randomized Conditions:

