Treatment Fidelity. Due to the open, group-like nature of physical therapy and patient confidentiality, we are unable to audio record treatment sessions. Therefore, to monitor treatment fidelity to ensure intended session content for both conditions is delivered and that unintended session content (i.e., contamination such as goal setting on physical activity levels with a patient randomized to PATH-12) is not delivered, physical therapists will complete a session checklist. In addition, random observations will occur by USC research staff. The physical therapist and observation fidelity checklists will monitor session duration, goals set, and indication if aerobic physical activity was discussed.

h. Data and Specimen Banking

NA

i. Statistical Analysis

Descriptive statistics will be used to describe baseline characteristics, establish recruitment and retention rates, and examine intervention intensity (session frequency, duration, and fidelity) and patient and therapist satisfaction. Mixed ANOVA or ANCOVAs, if appropriate adjustments are required based on baseline characteristics, will examine the changes in physical activity levels (MVPA/week, steps/day), and pain (PROMIS and WOMAC) across time between PATH and PATH-12. Additionally, differences between PATH and PATH-12 in physical function (chair stands, Timed Up and Go, 6-minute walk) will be examined at 12 weeks. Although the proposed study may not be powered to detect significant differences, the results will allow us to collect feasibility and acceptability data, refine the intervention, if necessary, and determine effect sizes for future grant submissions.

j. Data Management

All surveys will be administered either on paper or online via REDCap (secure, web application for building and managing online surveys and databases – managed by the University of South Carolina). Paper surveys will be stored in a locked filing cabinet at Palmetto Health-USC Orthopedic Center or the TecHealth Center at University of South Carolina. All computer files will be password protected. Only the study team will have access to the data.

k. Confidentiality

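### Section 7i should fix in advance an ANCOVA on own baseline, site and phase, state the number of sites, and use site-level intervals where there are enough sites

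*Combined protocol and SAP*

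**What the plan says.** Section 7i (Statistical Analysis) gives the method for activity and pain: "Mixed ANOVA or ANCOVAs, if appropriate adjustments are required based on baseline characteristics, will examine the changes in physical activity levels". No covariate is named, and the choice between the two methods rests on observed baseline characteristics. For function, "differences between PATH and PATH-12 in physical function (chair stands, Timed Up and Go, 6-minute walk) will be examined at 12 weeks", with no model given. Section 7f explains why there is no baseline for these tests: "Only at 12 weeks will participants complete functional tests". The results are meant to "determine effect sizes for future grant submissions".

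Section 7g (Design Overview) sets the structure that the analysis has to respect. First, "physical therapy sites will be randomized to either Immediate or Delayed". The first phase "will take place starting in November and end after 25 participants have been recruited". After a washout, "those sites randomized to Immediate will receive the PATH-12 intervention and those sites randomized to Delayed will receive the PATH intervention", until a further 25 patients have been recruited. This is a two-period cluster crossover with different patients in each period. No recruitment quota per site or per sequence is given. The number of sites, the intracluster correlation and an interval method are not stated.

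**The concern.** Three separate things follow from the wording.

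- **Precision.** A change-score test is a legitimate analysis but usually less precise than ANCOVA on the outcome's own baseline, which is already collected for activity and pain. Deciding on ANCOVA after seeing baseline comparisons also leaves the model open.
- **Phase.** Phase is tied to calendar time. If Immediate and Delayed sites recruit unequally, condition and phase are partly confounded, and a model without phase carries part of any phase difference into the treatment estimate.
- **Site.** A patient-level test treats 50 patients as independent although sites were randomized. Any site-by-phase variation makes the interval too narrow.

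At stake are the effect sizes and intervals carried into the next grant application.

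**Working it through.** The plan gives no power, correlation, intracluster correlation or number of sites, so there is no figure of its own to reproduce. All values of these quantities below are assumptions.

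**1. Two visits.** In a numerical check, the group-by-time F of the mixed ANOVA and the squared t of the change-score test were both 1.29388. They are the same test.

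**2. Precision.** Let the 12-week SD be 1, the baseline SD k, and the correlation rho. Change-score variance is 1 + k² − 2·rho·k and ANCOVA variance is 1 − rho². With k = 1 the ratio is (1 − rho²)/(2 − 2·rho) = (1 + rho)/2.

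| rho | change | ANCOVA | ratio |
|---|---|---|---|
| 0.3 | 1.40 | 0.91 | 0.65 |
| 0.5 | 1.00 | 0.75 | 0.75 |
| 0.7 | 0.60 | 0.51 | 0.85 |

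For k from 0.8 to 1.25 the ratio runs from 0.50 (rho 0.3, k 1.25: 0.91/1.8125) to 0.98 (rho 0.7, k 0.8: 0.51/0.52).

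**3. Phase.** Let Immediate sites supply a share p of each phase. The phase 1 share is then p among PATH patients and 1 − p among PATH-12 patients. Without phase in the model, the estimate moves by p − (1 − p) = 2p − 1 times the phase difference in change: 0.2, 0.4 and 0.6 of it at p = 0.6, 0.7 and 0.8. For an assumed 0.5 SD phase difference in the 12-week value (4 sites, rho 0.5), simulated shifts were 0.10, 0.20 and 0.29 SD, and 0.00 with phase in the model.

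**4. Site-by-phase variation.** With S sites there are 2S site-phase cells. Removing S site terms, one phase term and one condition term leaves S − 2 degrees of freedom: 0, 2 and 4 for 2, 4 and 6 sites. Site and phase main effects do not absorb this variation.

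Simulation with no treatment effect: 12,000 replicates per setting, 25 patients per phase spread at random over sites with at least one per cell, patient SD 1, site variance 0.05 at both visits, rho 0.5. Null rejection at nominal 5%:

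| Analysis | Sites | variance 0.02 | 0.05 | 0.10 |
|---|---|---|---|---|
| Planned change score | 2 | 7.7% | 12.0% | 17.3% |
| | 4 | 6.1% | 8.3% | 11.2% |
| | 6 | 6.0% | 7.4% | 9.2% |
| ANCOVA with site and phase, patient-level df | 2 | 8.6% | 13.9% | 21.3% |
| | 4 | 6.8% | 9.4% | 13.0% |
| | 6 | 6.5% | 7.5% | 10.3% |
| Site-level phase differences, S − 2 df | 4 or 6 | 4.8-5.3% throughout | | |

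With 2 sites the site-level test does not exist.

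**5. What the site-level analysis costs.** Its variance relative to the planned change score is 0.76-0.85, 0.89-0.98 and 0.95-1.09 at rho 0.3, 0.5 and 0.7, so the gain in step 2 shrinks and is about nil at high rho. At rho 0.5, typical 95% half-widths are about 1.0-1.25 SD with 4 sites (t = 4.30) and 0.74-0.85 SD with 6 (t = 2.78), against about 0.53 SD (0.52-0.54) at patient level.

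Uneven recruitment costs more. Adjusting for sequence and phase multiplies the variance by 1/(4p(1 − p)), which is 1/0.64 = 1.56 at p = 0.8. That outweighs the ANCOVA gain at rho 0.5 (1.56 × 0.75 = 1.17). With the split between sites left to chance, the simulated net rise over the planned test is about 25-30%.

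**The case against.** The strongest reply is that these are secondary outcomes of a feasibility pilot, and Section 7i already concedes that it may lack power. That stands, and it sets the weight.

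Several further points also stand:

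- The remedy is not free. Honest intervals with 4 sites are about twice as wide as patient-level ones, and part of the ANCOVA gain is lost.
- Below four sites it offers a caveat, not a valid interval. With 2 sites, adding site and phase at patient level gives slightly more null rejection than the planned test.
- Empty cells are possible. With 25 patients per phase, about 12% of trials with six equal sites would have at least one empty site-phase cell. With assumed recruitment weights of 4:3:2:1 over four sites it is about 15%, and with 4:3:3:2:2:1 over six about 41%.
- A seasonal shift common to both visits cancels in a change score. It does not cancel for the function tests, which have no baseline.
- The phrase about baseline characteristics could be meant to include the outcome's own baseline, but the plan does not say so.

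A reader might be tempted to take a much larger gain from the steps/day SDs in Table 1 of the Preliminary Studies: pooled 2948 at baseline and 1669 at 12 weeks give variance ratios of 0.30-0.32. The documents do not support this. The table is titled "Physical Activity Pre- and Post-Surgery in PACE", so its baseline precedes surgery, whereas Section 7f places this trial's baseline after surgery. It also comes from another study with 13 patients.

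**Conclusion.** The point holds as a cheap improvement to secondary analyses, of minor to moderate weight. What rests on the text alone is that the default is a change-score test, ANCOVA is conditional, and own baseline, site and phase are unnamed in a design that randomizes sites and switches them between phases. The sizes rest on assumed correlation, number of sites, variance components, recruitment share and phase difference, with normal data and no dropout in the simulation.

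A reader might infer that the planned estimates are biased or the planned test invalid. The documents do not show that. They give no recruitment split, no phase difference and no site-by-phase variance, and if these are negligible the planned test keeps its level. Nor do they establish that sites are few, since the number is not given. The ANCOVA gain itself assumes that baseline imbalance is due to chance. Therapists identify patients after their site's condition is set; if that makes imbalance systematic, ANCOVA and change scores can disagree and neither is fully protected.

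**What to change.** State the number of sites, and replace the model sentences in Section 7i with:

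> Each outcome measured at both visits will be analysed as the 12-week value on condition, its own baseline value, site and study phase, fixed in advance and not chosen from baseline comparisons. Chair stands, Timed Up and Go and 6-minute walk will be compared at 12 weeks with site and phase in the model.

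Then add the interval rule:

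- **Four or more sites with patients in both phases:** take each site's phase 1 minus phase 2 difference in baseline-adjusted means (unadjusted for the function tests). Compare Immediate with Delayed sites on (contributing sites − 2) degrees of freedom; half the difference between the two averages estimates the effect. Sites with an empty phase drop out and should be reported.
- **Fewer:** no site-level interval is practical. Report estimates as exploratory and say that patient-level intervals may be too narrow.

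Also confirm that the baseline activity value precedes any PATH content. Monitors are worn for 7 days, the background section puts therapy at 2-3 sessions a week, and Section 7g delivers PATH content at each session, so the window may include treated days. A change score would share this problem.

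The change needs wording and code only, with no new data or visits. The price is wider intervals and, with very uneven recruitment (p about 0.8), roughly 25-30% more variance in exchange for removing the phase shift.

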identified by Palmetto Health Physical Therapists will be provided information about the study verbally by a USC research staff member. Interested patients will be able to ask questions and read the consent form. They will have the opportunity to complete the informed consent process either at the first or second outpatient physical therapy appointment.

b. Inclusion and Exclusion Criteria

After initial identification of potential patient participants by physical therapists, research staff will screen patients for eligibility criteria in-person or over the telephone.

Inclusion criteria:

Eligible participants will 1) be 40-79 years of age, 2) have had a knee replacement in the last 2 months, 3) be willing to wear an accelerometer for 7 days during assessments, and 4) be English speaking.

Exclusion criteria:

As all patients will be under physicians' supervision post-TKR, participants will only be excluded if they (1) have any contraindications to activity, (2) have a mobility limiting comorbidity (e.g. spinal stenosis), or (3) have a scheduled surgery (i.e., TKR on contralateral knee) within the next 6 months.

c. Local Number of Subjects

We will aim to randomize 50 patients that had a knee replacement within the last 2 months and are attending outpatient physical therapy at the Palmetto Health USC Orthopedic Center. We anticipate that we will need to approach and screen approximately 75 patients to enroll our goal of 50 patients.

d. Study-Wide Number of Subjects

NA

e. Study Timelines

Subject participation will last 12 weeks. We estimate it will take 15 months to complete the study, which will include finished study enrollment, data collection and data analysis (See Figure 1).

Figure 1. Project Timeline

	Project Month														
	1	2	3	4	5	6	7	8	9	10	11	12	13	14	15
Finalize protocol & IRB approval	X	X	X												
Recruit TKA patients (n=50)				X	X	X	X	X	X	X	X	X	X		
Intervention				X	X	X	X	X	X	X	X	X	X		
Completing 12 week assessments				X	X	X	X	X	X	X	X	X	X	X	
Data Analysis														X	X
Prepare manuscript & presentations														X	X
Draft & submit NIH R21 or R01														X	X

f. Study Endpoints

[figure not shown]

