- Physical activity will be measured using Actigraph Link accelerometers owned by the TecHealth Center at the University of South Carolina. During assessments, participants will be asked to wear the Actigraph on their waist for 7 days. Non-wear time will be defined as ≥ 90 minutes with zero activity counts, allowing for up to 2 minutes of <100 counts/min.²⁶ Physical activity will be categorized as light (100-2019 counts/min) and moderate-to-vigorous (MVPA) (≥ 2020 counts/min).²⁷ Total MVPA over the week will be calculated. Steps/day will also be obtained. A valid day will be considered if participants wore the accelerometer for at least 10 hours/day. Participants will also be asked to complete a log indicating times the accelerometer was worn and taken off over the 7-day assessment period.
- Sedentary time will be measured using ActivPAL™ (PAL Technologies Ltd, Glasgow, UK), a small lightweight (15 g) uni-axial accelerometer. The time spent sitting/lying, standing, and walking, transitions and step counts will be determined. The ActivPAL summarizes data in 15 second intervals over 24 hours at a sampling frequency of 10 Hz.²⁸ During assessments, participants will be asked to wear the ActivPAL on their thigh for 7 days. Participants will also be asked to complete a log indicating times the ActivPAL was worn and taken off over the 7-day assessment period.
- Physical function measures will include the chair stand, timed up and go, and 6-minute walk test. All physical function tests will be completed following Osteoarthritis Research Society International (OARSI) recommendation procedures.²⁹ During the chair stand test, patients are asked to complete as many chair stand repetitions as possible during a 30-second period. The Timed Up and Go Test assesses the time in seconds taken to rise from a chair, walk 3-meters, turn, walk back to the chair, and sit down. The Six Minute Walk Test evaluates the maximal distance a patient can cover during a 6-minute period.
- Patient-Reported Outcomes will be assessed using two methods: 1) Patient-Reported Outcomes Measurement Information System (PROMIS)³⁰ utilizes a computer adaptive test via RedCap.³¹ We will assess pain intensity, pain interference, and mobility; 2) Western Ontario and McMaster Universities Arthritis Index (WOMAC) is a 15-item survey assessing pain and stiffness over the last 48-hour on a 5-point Likert scale.³²

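### Pilot MVPA minutes are strongly right-skewed, yet the MVPA/week analysis makes no provision for skew and leaves baseline adjustment optional

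*Combined protocol and SAP*

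**What the plan says.** Section 7 i (Statistical Analysis) gives the whole method for the activity outcomes in one clause: "Mixed ANOVA or ANCOVAs, if appropriate adjustments are required based on baseline characteristics, will examine the changes in physical activity levels (MVPA/week, steps/day". Pain outcomes follow in the same sentence. Nothing is said about transformation, ranks, a generalised linear or two-part model, or what happens if the distribution is unsuitable. ANCOVA is conditional on what the baseline data look like, and baseline MVPA is not named as a covariate.

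Section 7 f (Secondary Outcomes) defines the variable: "Total MVPA over the week will be calculated". No later text changes that scale, so analysis in minutes is the natural reading, although the plan does not state it outright.

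The only MVPA data in the document are in Table 1 of the Preliminary Studies, titled "Physical Activity Pre- and Post-Surgery in PACE (n=6) & Delayed PACE (n=7"), where the row is labelled "Bouted MVPA, min/week".

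On size and design: "We will aim to randomize 50 patients" (section 7 c) and "we have opted to randomize physical therapy sites instead of individual patients" (section 7 g). On power: "Although the proposed study may not be powered to detect significant differences" (section 7 i). That sentence goes on to say that the results will supply effect sizes for later grant applications.

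**The concern.** Minutes of MVPA cannot be negative. An SD larger than the mean in such a variable implies a long right tail, with most patients near zero and a few far above the rest. A mean difference in minutes then depends heavily on which arm the few active patients fall in, and a standardised effect size inherits an SD set by the same patients.

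The pilot's stated use of these results is to provide effect sizes for a later trial, so an unstable estimate matters even though significance is not the goal. Leaving baseline adjustment optional adds to the problem: the mixed-ANOVA group-by-time test on two visits is a t-test on the change score, which is usually less precise than ANCOVA on baseline. Deciding between the two after seeing the baseline data also leaves the method open.

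**Working it through.** The plan contains no power or sample-size calculation, so there is no figure of its own to reproduce.

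**Step 1. Skew in Table 1.** CV = SD/mean. For non-negative values the sum of squares cannot exceed the maximum times the sum. The share of all minutes supplied by the most active patient is therefore at least 1/n + (n − 1)·CV²/n². The largest possible CV is √n: 2.45 for n = 6 and 2.65 for n = 7.

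| Cell | Mean ± SD | CV | Top patient's share, at least |
|---|---|---|---|
| PACE baseline | 81.2 ± 141.8 | 1.75 | 59% |
| PACE 12 weeks | 3.5 ± 5.4 | 1.54 | 50% |
| PACE 26 weeks | 33.3 ± 76.4 | 2.29 | 90% |
| Delayed PACE baseline | 37.6 ± 85.7 | 2.28 | 78% |
| Delayed PACE 12 weeks | 62.1 ± 135.8 | 2.19 | 73% |
| Delayed PACE 26 weeks | 78.1 ± 108.0 | 1.38 | 38% |

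Example, PACE at 26 weeks: 1/6 + 5 × 2.294²/36 = 0.167 + 0.731 = 0.898. These bounds need no distributional model. They take the group sizes in the table title as holding at every visit; fewer patients at a visit would raise the bound.

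Steps/day behaves differently. The six CVs run from 0.33 to 0.58; the lowest is "4943.6±1653.2", 1653.2/4943.6 = 0.33.

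**Step 2. Power under a lognormal model.** The document gives no alpha, effect size, pre-post correlation or dropout rate. Assumed here: 25 per arm, two-sided 5%, correlation 0.5 on the log scale, a doubling of minutes, no zeros, independent patients, 10,000 replicates per row (Monte Carlo standard error at most 0.5 points). The last column is 1 − raw ANCOVA/rank ANCOVA.

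| SD/mean | Change score (mixed ANOVA) | Raw ANCOVA | Rank ANCOVA | Relative loss |
|---|---|---|---|---|
| 0.8 | 89.5% | 91.7% | 96.2% | 5% |
| 1.0 | 73.0% | 77.2% | 89.5% | 14% |
| 1.4 | 44.8% | 50.9% | 71.5% | 29% |
| 2.2 | 22.9% | 27.0% | 51.2% | 47% |

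In each row raw ANCOVA is ahead of the change-score test. With no true effect, the two raw tests reject in 3.5% to 4.8% of replicates and the rank test in 5.0% to 5.2%.

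**Step 3. Zeros.** Let the lowest 30% or 50% of values be zero at each visit, with the intervention doubling minutes only among active patients (SD/mean is before zeros are set).

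| Zeros | SD/mean | Raw ANCOVA | Rank ANCOVA |
|---|---|---|---|
| 30% | 1.4 | 41.1% | 41.0% |
| 30% | 2.2 | 23.9% | 29.0% |
| 50% | 1.4 | 29.3% | 18.7% |
| 50% | 2.2 | 18.6% | 14.2% |

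If instead the intervention halves the share of zeros and doubles minutes, rank ANCOVA does at least as well: 58.7% against 34.3% with zeros falling from 20% to 10% at SD/mean 2.3, and 85.4% against 85.5% with zeros falling from 40% to 20% at SD/mean 1.4. Neither method wins under every plausible model.

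**The case against.** The strongest reply has four parts.

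- **The pilot variable is not the trial variable.** Table 1 is bouted MVPA; the trial sums all minutes at or above the threshold, which should give fewer zeros and less skew. With 6 and 7 patients, CVs near the √n ceiling may reflect one person per cell. This stands, and it is why the lower rows of the power table matter.
- **The study is a feasibility pilot.** Feasibility and acceptability are primary, and the plan concedes low power. This also stands, but it does not cover the estimate of effect that the plan means to carry forward.
- **A rank contrast is not in minutes** and does not give the mean and SD usually needed for sample size. This stands, and it is why the mean difference should be kept.
- **The rank advantage depends on the model.** It does, as Step 3 shows.

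Two stronger readings are tempting. A reader might infer that the plan forfeits a third to a half of its power on its main activity outcome. The documents do not support that: they give no inputs for a power figure, the loss depends on the assumed distribution and effect, and MVPA/week stands beside steps/day as a secondary outcome with no ranking. A reader might also infer that the planned tests are invalid. In the simulations without a true effect they were slightly conservative, not inflated.

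**Conclusion.** The concern holds in a limited form. The sponsor's own MVPA data are strongly skewed, the plan has no provision for that, and baseline adjustment is left open. An MVPA effect size from about 25 patients per arm could rest on a few active patients.

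The cost in power is conditional: about 29% to 47% relative to rank ANCOVA if the trial's MVPA is as skewed as the pilot's (SD/mean 1.4 to 2.2), about 5% to 14% if it is milder (0.8 to 1.0), and none or a gain for the raw analysis if many patients stay at zero. These figures assume lognormal minutes that double, a correlation of 0.5 and independent patients. Because sites are randomised and switch condition between phases, the absolute powers do not describe this trial. The skew in Table 1 depends on none of these assumptions, but its carry-over to total MVPA is an inference.

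**What to change.** In section 7 i, for MVPA/week:

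- Always adjust for baseline MVPA by ANCOVA, in place of the mixed-ANOVA change test.
- Prespecify, alongside it, a rank-based ANCOVA of 12-week MVPA on baseline MVPA.
- Report medians, IQRs, a Hodges-Lehmann difference, and the share of zero-minute patients by arm and visit.
- Keep the mean difference in minutes, with a bootstrap 95% confidence interval whose resampling respects site, for planning the later trial. The number of sites is not stated; if it is very small, say what the interval can and cannot reflect about variation between sites.

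Keep natural-scale ANCOVA for steps/day, where the pilot SDs are well below the means.

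The cost is two or three sentences and no new data. The downside is two MVPA summaries to report, one of which (the rank test) is not in minutes.
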